#### C. PRELIMINARY DATA

Cardiovascular effects of DASH/SRD: In our DASH-DHF pilot study, 13 older adults (age 72±10 years) with compensated HF, HTN, and metabolic syndrome consumed a provided DASH/SRD for 21 days. 24-hour BP monitoring, blood and urinary analyses, transthoracic echocardiography, and cfPWV were completed pre- and post-DASH/SRD. Echocardiographic measures of ventricular-arterial coupling (Ees:Ea ratio), which measures the efficiency of blood transfer from the heart to the arterial tree, were obtained. We assessed ventricular

contractility via pressure-normalized wall stress, which strongly predicts mortality in HFpEF (Zhong et al. 2013). Diastolic function was evaluated with the Parametrized Diastolic Formalism. This kinematic model of ventricular filling analyzes early mitral inflow ("E-wave") patterns to quantify diastolic function via relaxation (*c*) and stiffness-based (*k*) constants. The close relationships between *k* and *c*, ventricular filling pressures, and cardiac mechanics have been invasively validated (Chung et al. 2015).

Food diaries demonstrated excellent DASH/SRD adherence, corroborated by decreased urinary sodium (3352±1593 to 1478±933 mg/24h; p<0.001) and increased urinary potassium excretion (2284±793 to 2925±1024 mg/24h; p=0.04). Despite treatment with multiple antihypertensives in nearly all subjects and overall well-controlled baseline BP, the DASH/SRD reduced 24-hour mean BP from 89±10 to 84±9 mmHg; p=0.04; cfPWV declined from 12.4±3.0 to 11.0±2.2 m/s; p=0.03. The DASH/SRD significantly improved ventricular stiffness and relaxation, while contractility and ventricular-arterial coupling ratio increased (*Figure 3*) (Hummel et al. 2013). Despite

[figure not shown]
Figure 3: DASH/SRD effects in HF V-A coupling Contractility 400 Ea: Ees ratio 년 100 왕 Baseline Relaxation constant Stiffness constant 60 600  $(g/s^2)$ ¥ 200 DASH/SRD DASH/SRD Baseline Whiskers: ± SD; \*: p < 0.05

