Sample size and power: The sample size is based on a combination of logistical considerations and power required to detect important differences in the primary endpoint of change in cfPWV in the context of a randomized crossover design. Sample size is based on a 2-sequence, 2-period, 2-treatment crossover design for continuous endpoints (using paired t test for mean differences). We conservatively assume a within-subject correlation of 0.70 for cfPWV measurements, based on our DASH-DHF pilot (0.81) and literature showing same-day correlation >0.90 (Wimmer et al. 2007) using the Sphygmocor device. We also assume approximate 10% dropout rate during Phase 1 of our study. Under these assumptions and using a two-sided type I error rate of 5%, 100 subjects, 50 allocated to the DASH/SRD-control diet sequence and 50 allocated to the control-DASH/SRD diet sequence, provides >80% power to detect an effect size (mean treatment difference/standard deviation) of 0.22 and >90% power to detect an effect size of 0.26. For comparison purposes, the effect size of cfPWV changes with DASH/SRD in our preliminary work in HFpEF has been 0.4-0.6; in dietary sodium restriction studies in healthier populations than we plan to study, the effect size is at least 0.2-0.4 (Seals et al. 2001, Todd et al. 2010). This sample size provides >80% power to detect an effect size of 0.5 in cfPWV change between salt-sensitive vs. salt-resistant subjects. This is a between-groups comparison based on a two-sample t test and two-sided Type I error of 5%.

Analysis plan: We will examine the distributions of outcomes under each treatment (e.g., DASH/SRD and control diet), as well as by salt-sensitive phenotype. Graphical approaches such as boxplots and scatterplots will be used, allowing identification of outliers, linearity, and correlation of measurements within subject and across time. If the distributional assumptions of our models are not met, transformations will be employed.

Obvious outliers unrelated to data entry error will prompt reconfirmation of acquisition methods and quality by another blinded investigator. We expect no carryover effects due to the two week duration of each dietary segment, a sufficient interval to match sodium intake and excretion even in subjects with chronic kidney disease (McMahon et al. 2013), who have more difficulty achieving this balance.

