Potential problems/alternative approaches: Despite our previous experience in collecting 24-hour BP and urinary data, it is possible that some attempts could be incomplete. If this occurs, the dietary intervention would be continued for an additional 24 hours to repeat the measurement. If despite these efforts, one or both of the 24-hour BP or urine collection are unacceptable in an individual, we would assign the salt-sensitive phenotype if clinic-measured mean BP is >5 mmHg higher following the control diet vs. the DASH/SRD segment; this threshold has been previously used to define salt-sensitivity in metabolic syndrome (Chen et al. 2009). This could affect the distribution of salt-sensitivity slightly, but we expect that few patients will have incomplete data and there will be no bias in missing data by underlying phenotype. The detectable effect size would increase based on the degree of imbalance between the number of subjects defined as salt-sensitive vs salt-resistant. In the event that this imbalance is as high as 70%:30%, the detectable effect size with >80% power would be 0.62 with a two-sided Type I error of 5%. If the distribution of salt-sensitivity is markedly different than expected, we would perform a secondary analysis using the median value or other appropriate cutpoint of the quantitative Sodium Sensitivity Index (Castiglioni et al. 2011).

We do not expect substantial difficulty in obtaining cardiovascular measures; [name] is evaluating all proposed echocardiographic parameters in four ongoing studies, including two NIH-funded studies using DASH/SRD as the intervention. A major focus of [name] NIH/NHLBI K23 award has been non-invasive vascular assessment. In the event that one or more of the cardiovascular measures cannot be obtained, multiple imputation methods will be used. In the course of studies conducted by [name] team, >120 subjects have completed dietary interventions, involving provided food and/or dietary counseling, lasting three weeks to four months. Adherence to provided meals has been excellent overall, but it is likely that some non-adherence will occur. The primary analysis will be intent-to-treat; if any subjects are severely nonadherent (via 24-hour urinary sodium or food diary review) we would do secondary analyses excluding these participants.

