Sample size and power: The sample size for *Phase 2* is set by the goals of *Aim 1* and influenced by drop-out during the 6 months of the interventions to promote DASH/SRD adoption. We assume that an additional 10% of subjects will drop out during *Phase 2* and that the dropout rate will be equal in salt-sensitive and salt-resistant participants, resulting in 90 subjects with evaluable data. The primary outcome of *Aim 2* of this proposal is the DASH/SRD concordance score from the Block Food Frequency Questionnaire in participants assigned to the WHEELS-I group vs. motivational interviewing alone. Based on national survey data and our preliminary work, we expect the mean baseline (Week 2 visit) dietary score to be 2.5±1.5. A sample size of 90 provides >80% power to detect an intra-group change of 0.6 between baseline and the end of study, based on paired t-testing two-sided Type I error of 5%. This sample size provides >80% power to detect a differential between group change in dietary score of 0.9, based on a two-sample t test and two-sided Type I error of 5%.

With regard to cardiovascular parameters, a sample size of 90 provides >80% power to detect an effect size of 0.6 in the primary endpoint of change from baseline to month 6 in LVMI between salt-sensitive vs. salt-resistant subjects (assuming a 50:50 split of salt sensitive vs. salt-resistant participants), with a two-sided Type I error of

5%. This between-groups comparison is based on a two-sample t test. Conservatively assuming that the standard deviation of the change in LVMI between baseline and 6 months ranges between 4 to 7 g/m2.7 (Blumenthal et al. 2010), this effect size translates to mean group differences of 2.4 to 4.2 g/m2.7. This would represent a 5-10% decrease in LVMI from baseline in salt-sensitive subjects (vs. no change in salt-resistant), similar to that in previous studies of dietary sodium restriction (Jula et al. 1994, Liebson et al. 1995).

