Analysis plan: Paired and 2-sample t-testing will be used to analyze changes in DASH/SRD concordance score as above, as well as changes in 24-hour urinary sodium excretion. The methods to analyze cardiovascular changes in *Aim 2* will be identical to those used in the comparison of salt sensitivity phenotypes in *Aim 1* (see above). Important covariates in the models to compare changes in cardiovascular parameters by salt-sensitive/resistant phenotype will be the degree of DASH/SRD concordance and changes in 24-hour BP.

Potential problems/alternative approaches: While motivational interviewing and the WHEELS-I program have been effective in our preliminary studies, we expect individual variance in DASH/SRD adoption. The primary analysis will be an intent-to-treat framework; secondary analyses will test interaction with the level of DASH/SRD adoption. (Mellen et al. 2008) We expect that participants who successfully adopt DASH/SRD will substantially change their eating habits. The WHEELS-I program does not target weight loss, but since sodium intake correlates with caloric intake (Guenther et al. 2013) it is possible that some veterans may lose weight during *Phase 2*. We do not a *priori* expect differential weight loss in salt-sensitive and salt-resistant subjects. However, since cfPWV and LVMI can both be reduced through weight loss, we will perform analyses adjusted for *Phase 2* weight changes (Blumenthal et al. 2010). If the proportions of salt-sensitive and salt-resistant subjects are not equal (say 60%:40%), we would retain >80% power to detect effect size of 0.61.

Specific Aim 3 (spans Study Phases 1 and 2): Determine effects of DASH/SRD feeding and longer-term adoption on microvascular function, and assess the relationship between endothelial glycocalyx integrity/sodium buffering and cardiovascular response to DASH/SRD.

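### The two Phase 1 power figures for salt-sensitive versus salt-resistant subjects (0.5, and 0.62 at a 70:30 split) cannot both be right on one SD scale, and the SD behind them is not named

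*Protocol*

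**What the plan says.** Protocol, D. APPROACH, Study phase 1, Sample size and power, gives two sets of figures for 100 subjects at two-sided 5%.

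- **Diet main effect (paired t test, within-subject correlation 0.70):** more than 80% power for "an effect size (mean treatment difference/standard deviation) of 0.22 and >90% power to detect an effect size of 0.26". This is the only definition of effect size, and it does not say which standard deviation. For comparison the section adds that "the effect size of cfPWV changes with DASH/SRD in our preliminary work in HFpEF has been 0.4-0.6".
- **Phenotype comparison (two-sample t test):** "This sample size provides >80% power to detect an effect size of 0.5 in cfPWV change between salt-sensitive vs. salt-resistant subjects". No standard deviation and no split are given. The SAP's Statistical Plan repeats this sentence.

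The Phase 1 section on potential problems and alternative approaches then says "The detectable effect size would increase based on the degree of imbalance", and continues: "In the event that this imbalance is as high as 70%:30%, the detectable effect size with >80% power would be 0.62". The SAP does not carry this figure.

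Phase 1 study design expects 30-50% of participants to be salt-sensitive under a cut of 8 mmHg in 24-hour mean BP, but does not tie that range to the power figure.

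For the Phase 2 phenotype comparison of LVMI (n = 90), the protocol is more explicit. It names a 50:50 split for an effect size of 0.6 and identifies the SD: "Conservatively assuming that the standard deviation of the change in LVMI between baseline and 6 months ranges between 4 to 7" (g/m^2.7). For 60:40 it says "we would retain >80% power to detect effect size of 0.61".

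**The concern.** The 0.62 is offered as the price of imbalance, so it should be the balanced detectable effect multiplied by a known factor. It is too large for that if 0.5 is near the balanced limit. If 0.5 is instead well above the limit, 0.62 is too large to be the limit at 70:30.

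This matters because the SAP makes salt-sensitive versus non-salt-sensitive the Phase 1 comparison, and 0.5 is its only power figure for it. Someone reading a null phenotype difference in cfPWV needs to know whether a 0.5 effect would have been missed about one time in eight or about one time in three. An SAP reader does not see the 0.62, and so has no sign of the conflict.

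**Working it through.** **Inputs.** n = 100, two-sided 5%, two-sample t test, correlation 0.70 (Protocol, Study phase 1, Sample size and power). Splits from 50:50 to 70:30 (30-50% salt-sensitive, Phase 1 study design). The 100 is taken as evaluable: 110 enrolled less about 10% dropout is about 99.

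**Method.** Power from the noncentral t distribution with n1 + n2 - 2 degrees of freedom and noncentrality d × sqrt(n1·n2/(n1 + n2)), where d is the difference in SDs of the change. At correlation 0.70, SD of the change = sqrt(2 × (1 - 0.70)) = 0.775 single-visit SDs. An effect of 0.5 single-visit SDs is therefore d = 0.5/0.775 = 0.645.

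**Step 1: which scale reproduces the plan's other figures?**

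| Stated figure | SDs of the change | Single-visit SDs, corr. 0.70 |
|---|---|---|
| 0.22, main effect, >80% | 58.7% | 80.3% |
| 0.26, main effect, >90% | 73.1% | 91.4% |
| 0.62 at 70:30, n = 100 | 80.3% (limit 0.617) | 95.3% (limit 0.478) |
| Phase 2: 0.6 at 50:50, n = 90 | 80.4% | not applicable (SD of change named) |
| Phase 2: 0.61 at 60:40, n = 90 | 80.1% | not applicable |

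The main-effect figures are in single-visit SDs. The other phenotype figures match SDs of the change.

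**Step 2: the 0.5 on each scale.**

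| Split | Power for 0.5, SDs of change | 80% limit | Power for 0.5, single-visit SDs | 80% limit |
|---|---|---|---|---|
| 50:50 | 69.7% | 0.566 | 89.2% | 0.438 |
| 60:40 | 67.9% | 0.578 | 87.9% | 0.447 |
| 70:30 | 62.1% | 0.617 | 83.4% | 0.478 |

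With the pilot's correlation of 0.81 the single-visit powers rise to 98.0%, 97.6% and 95.7%, and the 70:30 limit falls to 0.381, further from 0.62.

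**Step 3: a check that does not depend on the scale.** Going from 50:50 to 70:30 multiplies the detectable effect by sqrt((1/30 + 1/70)/(1/50 + 1/50)) = 1.091. So 0.5 would become 0.546, and 0.62 would come from 0.62/1.091 = 0.568. The stated ratio is 0.62/0.5 = 1.24; even with generous rounding (0.615/0.549) it is 1.12.

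**Step 4: can another setting rescue 0.5 in SDs of the change?** At 50:50:

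- Largest value that rounds to 0.5 (0.549): 77.6%.
- n = 110: 73.8%. n = 90: 65.0%.
- One-sided 5%: 79.9%. But the plan says two-sided, and the one-sided 70:30 limit would be 0.546, not 0.62.
- 80% power for 0.5 would need 128 subjects (50:50), 133 (60:40) or 152 (70:30).

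**Step 5: do the pilot data identify the scale?** The pilot reports that "cfPWV declined from 12.4±3.0 to 11.0±2.2 m/s", a fall of 1.4. In single-visit SDs this is 1.4/3.0 = 0.47 or 1.4/2.2 = 0.64, close to the quoted 0.4-0.6. With correlation 0.81, SD of the change = sqrt(9 + 4.84 - 2 × 0.81 × 6.6) = 1.77, giving 1.4/1.77 = 0.79, outside that range. This favours single-visit SDs for the main-effect paragraph, but it does not show which SD the phenotype sentence uses.

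**In m/s.** If the pilot SDs of 2.2-3.0 carry over (an assumption), 0.5 means 0.5 × 2.2 = 1.1 to 0.5 × 3.0 = 1.5 in single-visit SDs. In SDs of the change it means 0.85 to 1.16 (the same values times 0.775).

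**The case against.** The best defence is that both sentences claim only power above 80%. In single-visit SDs at correlation 0.70 both are literally true: 83-89% for 0.5, and 95% for 0.62 at 70:30. That scale also reproduces 0.22 and 0.26 in the same paragraph. Nor does the protocol call 0.5 a minimum detectable effect, so the 1.24 ratio alone does not show that 0.5 is wrong. All of this stands, and it is why 0.5 cannot be called an error outright. It does not rescue the text, because the protocol presents 0.62 as the detectable effect that results from imbalance. On the single-visit scale that value is 0.48.

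A second point is that the SAP analyses Phase 1 by regression adjusted for baseline, which could raise power. With correlation 0.70 and no baseline cfPWV difference between phenotypes, power for 0.5 would be about 77% to 69% in SDs of the change, still below 80%, and 93% to 89% in single-visit SDs. The condition is doubtful, since the Background reports abnormal arterial stiffness in salt-sensitive subjects. The documents also attach the 0.5 to an unadjusted two-sample t test, so that is the test to check it against.

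Third, the SAP describes a study already conducted, so no design decision changes. That is true and limits the severity, but a power statement that supports the reading of a null result should still be correct.

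Finally, the pilot's 0.79 sits uneasily with its reported p = 0.03. If that p came from a paired t test on 13 subjects, t is about 2.46, the SD of the change is about 2.05 and the effect size about 0.68. This too lies outside 0.4-0.6, so the inference is the same.

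**Conclusion.** The concern holds. No single SD scale supports both 0.5 with more than 80% power and 0.62 as the 70:30 detectable effect.

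- **If SDs of the change were meant,** the 0.5 claim is wrong: power is 62-70%, a miss rate of 30-38%.
- **If single-visit SDs were meant,** the 0.5 claim is right (miss rate 11-17%) and the 0.62 should be 0.48.

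The documents do not settle which. The results rest on 100 evaluable subjects, an unadjusted two-sided 5% t test, splits from 50:50 to 70:30 and, for the single-visit scale, correlation 0.70.

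The 30-50% range belongs to the protocol's 8 mmHg cut. The SAP's definition of salt-sensitivity states no threshold, so the split it implies is unknown. At an assumed 20:80 split, power for 0.5 would be 50.8% in SDs of the change or 72.5% in single-visit SDs at correlation 0.70, below 80% on both.

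The point should be fixed. It affects how a null phenotype difference is read, not enrolment, the model or the estimates.

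**What to change.** In the protocol's Phase 1 sections on sample size and on potential problems, and in the SAP's Statistical Plan, name the SD and the split for every effect size and put the phenotype figures on one scale.

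- **If SD of the change:** replace the 0.5 sentence with wording such as: *100 subjects give 80% power for a between-phenotype effect of 0.57 (50:50) to 0.62 (70:30) SDs of the change; power for 0.5 is about 70% (50:50) to 62% (70:30).* Keep 0.62.
- **If single-visit SD:** keep the claim of more than 80% for 0.5, add *single-visit SDs, correlation 0.70, splits from 50:50 to 70:30*, and change 0.62 to 0.48.

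In the SAP, note that the 30-50% salt-sensitive range comes from the protocol's 8 mmHg cut. A baseline-adjusted power figure is best left out, because it would assume equal baseline cfPWV in the two phenotypes.

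The cost is wording in three places. On the first option a stated figure becomes less favourable. No extra patients, data or analyses are needed.

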#### D. APPROACH

General Design: This 7-month dietary intervention study will recruit from the Ann Arbor Veterans Affairs Health System and affiliated Community-Based Outpatient Clinics (CBOCs). We hypothesize that dietary modification with the DASH/SRD will improve HF-associated cardiovascular dysfunction in veterans with HTN and metabolic syndrome, and that differential improvements will occur in those with a salt-sensitive BP phenotype vs. those with salt-resistant BP. The study will take place in two phases (Figure 7): Phase 1 participants will consume their usual diet, followed by a DASH/SRD for 14 days each. Salt-sensitive vs. salt-resistant status will be defined by 24-hour BP measurement at the end of each segment In Phase 2, all participants will receive motivational interviewing-based dietary counseling; half will participate in WHEELS-I to promote DASH/SRD adoption over 6 months.

Participants will have a clinical evaluation at 4 time points (denoted by ↑ in *Figure 7* and described below): at weeks 2 and 4 of the *Phase 1* crossover intervention, and at 1 and 6 months of the *Phase 2* DASH/SRD adoption period.

The *Phase 1* primary analysis will evaluate cardiovascular functional changes during usual diet and DASH/SRD diet periods, and test for interaction with saltsensitivity status. Phase 2 will assess the performance of WHEELS-I in promoting DASH/SRD adoption, and evaluate cardiac structural changes between salt-sensitive and salt-resistant

Figure 7: Overall study timeline

Abbreviations: DASH/SRD, sodium-restricted Dietary Approaches to Stop Hypertension; SR, salt-resistant; SS, salt-sensitive; WHEELS-I, Womens' and Men's Hypertension Experiences and Emerging Lifestyles Intervention; **†** = Clinical visit (see text)

participants (as they were defined by BP measurement in *Phase 1*). After completion of *Phase 2*, telephone clinical and mailed dietary questionnaire follow-up will occur after 6 months. An optional, in-person visit may also be performed at this time to obtain arterial tonometry data and clinic blood pressure.

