- Safety Monitoring: Patients will perform home BP monitoring with their own personal cuff or a provided Omron 7 series automated cuff (Omron Healthcare, Lake Forest, IL). Monitoring will be daily during the run-in period and *Phase 1* of the study, and at least weekly thereafter if systolic BP is >180 or <100 mmHg on more than one occasion, or if symptoms suggest hyper- or hypovolemia (e.g., worsening/new edema, dizziness), the participant will be scheduled for an in-person safety visit. Targeted history and physical will be performed by a clinician-investigator, with laboratory or other testing obtained based on the clinical presentation. Antihypertensive medications may be adjusted at this visit if needed for participant safety. Safety visits may also be scheduled for worsening glycemic control in diabetic participants. See *Human Subjects Protection* section for additional details.

Study phase 1: Phenotype veterans with HTN and metabolic syndrome as salt-sensitive or salt-resistant; determine effects of a 2-week DASH/SRD intervention vs. control diet on HFpEF functional cardiovascular risk factors in salt sensitive compared to salt-resistant veterans.

Introduction: Animal models, cohort studies, and our preliminary work suggest that the DASH/SRD would favorably affect cardiovascular parameters that predict incident HFpEF in veterans with HTN and metabolic syndrome, and have a stronger effect in salt-sensitive individuals. Our working hypothesis is that the DASH/SRD will produce significantly greater improvement than control diet in HFpEF risk factors including large-arterial stiffness (carotid-femoral pulse wave velocity [cfPWV], primary outcome), left ventricular diastolic function, and left ventricular systolic function. We further hypothesize that the improvement in these measures will be greater in salt-sensitive veterans. We will test our hypotheses in a 2-sequence, 2-period, 2-treatment comparison of DASH/SRD vs. control diet.

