**Phase 1 study design:** Consented participants will have clinic BP measured at the screening visit and will enter a two-week usual diet period, during which antihypertensive medications, with the exception of calcium channel blockers, will be weaned off under [name] supervision and with guidance from daily home BP monitoring. During this time period, the participant will consume their usual diet. Potential subjects with ontreatment, resting, average systolic BP of > 160 mmHg at the screening visit will be excluded from further

participation, as will those with symptomatic hypertension or systolic BP of > 180 mmHg on more than one occasion during the ad-lib dietary period.

Following the usual diet period and the week 2 visit, participants will consume the DASH/SRD diet for 14 days each. This time period is sufficient to demonstrate changes in BP and arterial stiffness, which peak at 2 weeks after dietary sodium modification (Gates et al. 2004). In addition to in-clinic BP measurement, 24-hour ambulatory BP will be obtained at the end of each dietary sequence. We expect that the DASH/SRD will reduce BP across the cohort, but differentially on an individual basis (Sacks et al. 2001).

The salt-sensitive vs. salt-resistant phenotype will be defined as a change in 24-hour mean BP of ≥8 mmHg between control and DASH/SRD dietary segments (Castiglioni et al. 2011). Based on previous studies in patients with HTN, we expect that 30-50% of participants will be classified as salt-sensitive (Elijovich et al. 2016). The 24-hour ambulatory BP monitoring and 24-hour urinary collections will be used to provide an alternate definition of salt-sensitivity. Specifically, the quantitative Sodium Sensitivity Index will be calculated as the change in 24-hour mean BP divided by the change in 24-hour urinary sodium excretion between DASH/SRD and control diet periods (Castiglioni et al. 2011).

The *Phase 1* primary outcome is the cfPWV compared at the end of usual diet and DASH/SRD. This parameter was chosen because of its association with incident HF in community-dwelling elderly (Tsao et al. 2015) and its high sensitivity and specificity for HF in older adults with unexplained exertional dyspnea (Weber et al. 2013). Key secondary outcomes include ventricular diastolic function (k; ventricular stiffness) and systolic function (global longitudinal ventricular strain) and left atrial reservoir function (left atrial strain).

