An intention-to-treat approach will be used to analyze endpoints, including all randomized participants. Multiple imputation will be used for missing data, which assumes that outcome data are missing at random (i.e., where other variables from the study can account for differences in the primary outcome for observed and missing subjects) (Little et al. 2012). A linear mixed effects model (Verbeke et al. 2000, Diggle et al. 2013) will be used to assess the effect of intervention on the change in cfPWV, with fixed-effect terms for sequence, study period, dietary intervention, and adjusting for baseline cfPWV and other potential confounders, e.g. age, race, body mass index, diabetes status, and renal function. A random-effect term will be included to account for the correlated measurements for each subject. Tests to compare diet will be based on Wald and chi-squared tests based on maximum likelihood or restricted maximum likelihood methods. Alternative covariance structures (other than compound symmetry) will be explored and model fit will be examined using the Akaike Information Criteria (Holford 2004). This approach will also be used for the key secondary endpoints (ventricular diastolic stiffness k and global longitudinal ventricular strain) and other cardiovascular parameters (e.g. E/e' ratio). For binary secondary outcomes (e.g. serious adverse events) a similar mixed model approach will be employed (Ezzet et al. 1992). To test whether improvements in the primary and key secondary endpoints are greater in salt-sensitive than in salt-resistant subjects, interaction will be assessed via the linear mixed model described above, with a fixed-effect term for salt-sensitivity phenotype.

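### The only stated analysis of serious adverse events is a leftover crossover diet comparison in randomised participants; under the fixed diet order it cannot isolate diet, and it leaves out anyone who exits during Phase 1

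*Protocol*

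**What the plan says.** The Phase 1 analysis plan (Protocol, section D, Study phase 1) sets the population: "An intention-to-treat approach will be used to analyze endpoints, including all randomized participants". It then gives the linear mixed model for carotid-femoral pulse wave velocity, "with fixed-effect terms for sequence, study period, dietary intervention", plus covariates and a random subject effect. SAEs appear once, as an example: "For binary secondary outcomes (e.g. serious adverse events) a similar mixed model approach will be employed". The text available for review states no other SAE analysis.

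The design those sentences now serve is described elsewhere:

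- **Order of diets.** General Design: "Phase 1 participants will consume their usual diet, followed by a DASH/SRD for 14 days each". Phase 1 study design and the SAP give the same single order.
- **Drug weaning.** In the usual-diet period, "antihypertensive medications, with the exception of calcium channel blockers, will be weaned off". Prior therapy is restored around the start of Phase 2 (Phase 2, Dietary intervention).
- **Removal.** Phase 1 study design excludes people whose systolic pressure is above 160 mmHg at screening, "as will those with symptomatic hypertension or systolic BP of > 180 mmHg on more than one occasion during the ad-lib dietary period".
- **Randomisation.** Participants are randomised to WHEELS-I or control before the first Phase 2 visit. The SAP confirms that Phase 1 came before randomisation.
- **SAP.** Phase 1 outcomes are analysed by linear regression adjusted for baseline. No SAE or other safety analysis is given.

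**The concern.** The SAE sentence was written for a randomised two-sequence crossover. When the design became a single fixed order, the SAP changed the efficacy analysis, but the SAE sentence was left as it was. Two things follow if it is applied as written.

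First, it calls for a comparison of SAEs between diets that the design cannot support. Any difference between the two fortnights could reflect diet, time, or withdrawal of antihypertensive drugs.

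Second, its analysis set begins at a randomisation that happens after the drugs have been withdrawn and both diets completed. The people in whom weaning went worst are removed before that point. An SAE in one of them would fall outside the only SAE analysis described, and the result would describe only those who got through Phase 1.

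What is at stake is safety reporting, not the efficacy conclusions.

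**Working it through.** **1. The plan's own figure, for context.** No figure is attached to SAEs. The same Phase 1 plan gives power for a two-sequence crossover: 100 participants (50 + 50), within-subject correlation 0.70, two-sided 5%. With dz = d / √(2(1 − 0.70)) = d / 0.775:

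- d = 0.22: dz = 0.284, noncentrality 0.284 × √100 = 2.84, paired-t power 0.803.
- d = 0.26: dz = 0.336, noncentrality 3.36, power 0.914.

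The stated >80% and >90% reproduce. The calculation is labelled as a two-sequence crossover, which is also the design behind the SAE sentence.

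**2. Can the stated terms estimate a diet effect?** Take 100 participants × 2 periods and count the independent fixed-effect columns.

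| Design | Columns | Rank |
|---|---|---|
| 50/50 crossover | intercept, sequence, period, diet | 4 of 4 |
| Fixed order | intercept, sequence, period, diet | 2 of 4 |
| Fixed order | intercept, period, diet | 2 of 3 |
| Fixed order | intercept, diet | 2 of 2 |

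In the crossover the correlation of period with diet is 0. In the fixed order it is 1, and sequence takes a single value. A diet coefficient exists only when sequence and period are both removed, and it is then the difference between the second fortnight and the first.

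**3. What else differs between the fortnights.** The first contains the weaning. The second is spent off the weaned drugs, which return only around Phase 2. The before/after contrast therefore carries drug withdrawal as well as diet and time.

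The documents give no SAE rates, so the following is an illustration on assumed values only. Let the SAE risk per fortnight be 1–2%, with no true diet effect, and let weaning add 1–3 percentage points in the first fortnight among people who stay in the set. The apparent odds ratio for DASH/SRD against usual diet is [p0/(1 − p0)] / [p1/(1 − p1)], with p1 = p0 + the excess:

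- p0 = 1%, excess 3 points: (0.01/0.99) / (0.04/0.96) = 0.24.
- p0 = 2%, excess 1 point: (0.02/0.98) / (0.03/0.97) = 0.66.

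Over the assumed grid the range is 0.24 to 0.66. If the harm of being off drugs built up later, the distortion would run the other way. The direction is not known.

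**4. Who is in the set.** The steps in order are consent, usual diet with weaning (removals occur here), DASH/SRD, then randomisation to WHEELS-I. Anyone who leaves before the last step is not a randomised participant.

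The planning figures are 110 enrolled (Recruitment strategy), about 10% Phase 1 dropout (Phase 1, Sample size and power), and 90 evaluable after a further 10% (Phase 2, Sample size and power), which implies 100 entering Phase 2. If removals count as dropouts, 110 − 100 = 10 starters (10/110 = 9.1%) are never randomised for any reason, and the hypertension removals are somewhere between 0 and 10 of them. This is a limit from planning figures, not an estimate.

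**The case against.** The strongest case against runs as follows.

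- **It is residue that the later SAP has overtaken.** The SAP is written in the past tense, changes the Phase 1 model, and does not list SAEs as an outcome. Nothing shows that the SAE model was ever meant to survive. This stands as a caution: the point concerns what the plan states, not what was run. But the SAP puts nothing in its place.
- **The model is only described as similar.** An analyst could drop the unusable terms. True, but step 2 shows what then remains.
- **Randomised once meant randomised to diet sequence, in an efficacy sentence.** That is probably its origin. Under the current design no such randomisation exists, and no other set is stated for SAEs.
- **The removals are run-in failures.** Safety Monitoring mentions a run-in period, and the removal rule shares a sentence with a screening exclusion. The text is ambiguous. However, General Design and the SAP both place the usual diet inside Phase 1, and these people have consented and had drugs withdrawn under the protocol.
- **Safety reporting may be covered in Human Subjects Protection.** Safety Monitoring refers to that section, which was not available for review. This stands in full and makes part of the fix conditional.

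Three stronger readings are tempting, and the documents do not support them.

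- A reader might infer that the same blood pressure event removes a participant in one diet period and keeps them in the set in the other. Safety Monitoring says only that, "if systolic BP is >180 or <100 mmHg on more than one occasion", or if symptoms suggest a volume problem, "the participant will be scheduled for an in-person safety visit". It does not say whether a participant on DASH/SRD then continues, and anyone withdrawn at that point would also go unrandomised.
- A reader might count all 20 expected screen-fails as weaning removals, giving 30 of 130 never randomised. Recruitment strategy ties those 20 to screening visits, and the protocol lists many other exclusions.
- A reader might cite Phase 2's greater length as a fault. The stated model compares two equal 14-day periods, so it is not one.

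**Conclusion.** The point holds as a limited defect in the safety analysis, worth correcting. The one stated SAE rule does not fit the design in two respects. Its diet effect is not estimable with the named terms (rank 2 of 4) and is a confounded before/after contrast without them. Its analysis set excludes everyone who leaves during Phase 1, including people removed for symptomatic or repeated >180 mmHg hypertension during weaning.

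The conclusion rests on reading the SAE sentence together with the model and population stated just before it, and on WHEELS-I being the only current randomisation. The number of removals and the SAE rates are not given, so the practical effect cannot be sized. A reader might infer that the removals are themselves SAEs, that weaning caused them, or that they go unreported. The documents show none of these: events and safety visits are recorded, and the question is which denominator and comparison they enter.

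**What to change.** Delete SAEs from the diet-comparison mixed model in the Phase 1 analysis plan and add a short safety paragraph to the SAP:

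1. Safety set: all consented participants who start the usual-diet/weaning period.
2. Summarise SAEs descriptively by period (usual diet/weaning, DASH/SRD, Phase 2) and, within Phase 2, by randomised arm.
3. List the participants removed for hypertension in the usual-diet period, and say whether they are counted as dropouts or as screen-fails.
4. State that differences between the Phase 1 periods are not attributed to diet.

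If Human Subjects Protection already provides this reporting, cross-refer to it and only delete the sentence.

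The cost is one paragraph and a few tables. No new data are needed, since clinical events are updated at each visit and safety visits are part of the monitoring. A between-diet SAE p-value is lost, but it could not have been interpreted. The real downside is a safety denominator that differs from the efficacy one and must be labelled wherever it appears.
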